5.1.2. Analysis of Adverse Events

Number and percentage of subjects with at least one particular AE (unsolicited/solicited) will be tabulated. Unsolicited AEs will be summarized by System Organ Class and Preferred Term. Solicited AEs will be summarized by class (local, systemic) and preferred term.

For solicited AEs following tables will be provided: summary, by worst severity grade, grade 3, related (systemic only), time to onset (in days) and duration (in days) for most frequent events and body temperature. Note: Duration is defined as number of days from the start of the event until

resolution of the event. The time to first onset is defined as (date of first onset – reference date + 1). The reference date is the start date of the regimen period.

For unsolicited AEs following tables will be provided: summary table (including SAE, fatal outcome and discontinuation), all events, most frequent events, grade 3 events, events leading to permanent stop of vaccine, related events and SAEs. Potential adverse events of special interest (AESI) will be tabulated.

A summary of the solicited and unsolicited AEs will also be tabulated by subgroups of pre-existing Ad26 neutralizing antibody (<LLOQ, >=LLOQ). Refer to the subgroup definition in Section 2.4.

Listings and/or subject narratives will be provided as appropriate, for those subjects who die, discontinue study vaccinations due to an AE, or experience a severe or serious AE.

5.1.3. Phase Allocation of Adverse Events

Solicited events are always allocated to the respective Post Dose period. Solicited events are allocated to the phases as described below. However, they are always allocated to the respective post-dose period and will never be attributed to a screening or follow-up phase. Time is not considered while attributing solicited AEs to phases.

For the phase allocation of unsolicited AEs, the following steps will also be followed:

Step 1: Allocation of events to the periods:

Adverse events in the SDTM database are allocated to periods based on their start date/time. If the start date/time of an event falls between (or on) the start and stop date/time of a period, the AE is attributed to that period (treatment-emergent principle).

- In case of partial start or stop dates (i.e. time and/or day and/or month and/or year missing), the events are allocated to the periods using the available partial information on start and end date; no imputation will be done. If, for instance, the AE start date only month and year are available, these data are compared to the month and year information of the periods. This rule may lead to multiplication of the event as a consequence of its assignment to multiple periods.

- In case of a completely missing end date, the date is imputed by the cut-off date of the analysis for subjects still ongoing in the study, and by the end date of the last period for subjects who discontinued or completed the trial.

- In case of a completely missing start date, the event is allocated to the first active phase (post dose 1 period), except if the end date of the AE falls before the start of the first active phase (post dose 1 period).

Step 2: Combination of events:

Overlapping/consecutive events are defined as events of the same subject with the same preferred term which have at least 1 day overlap or for which the start date of an event is 1 day after the end

date of the preceding event. Overlapping/consecutive events may be combined into one AE or not, according to the following rules:

1) If overlapping/consecutive events start in one of the following periods - Screening or intermittent follow up (i.e. non-active periods) - followed by an AE in - post-dose period (active period) - they are allocated to their respective periods and are considered as separate events.

2) In case overlapping/consecutive events start within a single period, they are considered as one and the same AE. The individual events which contribute to this AE are retained as individual records in the ADaM database but are assigned the same onset, period, and total duration. All related attributes to the AE/phase/period should also be consistent with the new event.

3) In case overlapping/consecutive events start in both an active period followed by a non active period, they are allocated to the active period only and are considered as one and the same AE. The individual events which contribute to this AE are retained as individual records in the ADaM database but are assigned the same onset, treatment period, and total duration. All related attributes to the AE/phase/period should also be consistent with the new event.

4) In case an active period is followed by another active period, and the overlapping/consecutive events start in both periods, they are allocated to their respective period and are considered as separate AEs. In case overlapping/consecutive events start in non-consecutive periods (regardless of active or non-active), they are allocated to their respective period and are considered as separate AEs.

5) In case a non-active period is followed by another non-active period, and the overlapping/consecutive events start in both periods, they are allocated to the first period and they are considered as one and the same AE. The individual events which contribute to this AE are retained as individual records in the ADaM database but are assigned the same onset, period, and total duration. All related attributes to the AE/phase/period should also be consistent with the new event.

Remarks:

1. Events can only be combined into one and the same AE if their start and stop dates are known.
2. In case the completely missing end date is imputed (for period allocation), this date is also considered as a complete date.
3. Time is not considered when determining overlap of events.

AESI Analysis

Selection of potential AESIs (programmed definition):

Potential AESIs will be selected programmatically. Those will include all reported AEs that are identified by the selection rule:

- SMQ (Standardised MedDRA Queries) = “EMBOLIC AND THROMBOTIC EVENTS (SMQ)”
or
- (SUB_SMQ1 = “HAEMATOPOIETIC THROMBOCYTOPENIA (SMQ)” and SCOPE in ('BROAD', 'NARROW')) or HLT (higher level term) = “Thrombocytopenias”

Outputs:

Potential AESIs (programmed definition) will be summarized by Interest category and Preferred Term. The interest categories are:

- ‘Embolic and thrombotic events (SMQ)’
- ‘Haematopoietic Thrombocytopenias (SMQ) (broad) or HLT = Thrombocytopenias’.

Potential AESI determined programmatically, related to study vaccine (investigator assessment), will be tabulated similarly.

Those AESI analyses will be presented by phase as well as by time interval. The definition of the different time intervals can be found below.

For potential AESIs determined programmatically, attribution to the intervals will be done similarly to the unsolicited AEs as described in Section 5.1.3 above. For Step 2 of phase allocation of adverse events, the ‘0 - 28 days post-dose’ intervals should be treated similar to ‘active’ periods and the rest as ‘non- active’ periods.

The Definition of the time intervals is shown in the table below. Additionally, in the tables a ‘0-56 days post-dose’ interval and a ‘0-6 months post-dose’ interval should also be shown. The ‘0-56 days post-dose’ interval is the combination of the ‘0 - 28 days post-dose’ interval and the ‘29 - 56 days post-dose’ interval. The ‘0-6 months post-dose’ interval is the combination of the ‘0 - 28 days post-dose’ , ‘29 - 56 days post-dose’ and ‘57 days - 6 months post-dose’ intervals.

Definition of intervals:**SR1004 cohort 1/2**

Dose	Interval	From	to
Post-vaccination 1	0-28 days post dose	Date time of the 1 st vaccination	Min of: 
 • 23:59 at date of last contact (for discontinuations) • 23:59 at date of DB cut-off for interim analyses • Maximum(Date of Vaccination 1 + 28 days at 23:59, date of scheduled visit 4 weeks after 1st vaccination at 23:59)
	29-56 days post dose	One minute after the end of the interval 0-28 days post dose	Min of: 
 • 23:59 at date of last contact (for discontinuations) • 23:59 at date of DB cut-off for interim analyses • One minute prior to date time of vaccination 2
	57 days - 6 months post-dose #	One minute after the end of the interval 29-56 days post dose	Min of: 
 • 23:59 at date of last contact (for discontinuations) • 23:59 at date of DB cut-off for interim analyses

			
 • Date of Vaccination 1 + 183 days at 23:59
	>6 months post-dose #	One minute after the end of the interval 57 days - 6 months post-dose	Min of: 
 • 23:59 at the date of last contact (for discontinuations) • 23:59 at the date of DB cut-off for interim analyses • 1 minute prior to date time of Vaccination 3 *
Post-vaccination 2	0-28 days post dose	Date time of the 2nd vaccination	Min of: 
 • 23:59 at date of last contact (for discontinuations) • 23:59 at date of DB cut-off for interim analyses • Maximum(Date of Vaccination 2 + 28 days at 23:59, date of scheduled visit 4 weeks after 2nd vaccination at 23:59)
	29-56 days post dose	One minute after the end of the interval 0-28 days post dose	Min of: 
 • 23:59 at date of last contact (for discontinuations) • 23:59 at date of DB cut-off for interim analyses • Date of Vaccination 2 + 56 days at 23:59
	57 days - 6 months post-dose	One minute after the end of the interval 29-56 days post dose	Min of: 
 • 23:59 at date of last contact (for discontinuations) • 23:59 at date of DB cut-off for interim analyses • Date of Vaccination 2 + 183 days at 23:59
	>6 months post-dose	One minute after the end of the interval 57 days - 6 months post-dose	Min of: 
 • 23:59 at the date of last contact (for discontinuations) • 23:59 at the date of DB cut-off for interim analyses • 1 minute prior to date time of Vaccination 3 *
Post-vaccination M12*	0-28 days post dose	Date time of the 3rd vaccination	Min of: 
 • 23:59 at date of last contact (for discontinuations) • 23:59 at date of DB cut-off for interim analyses • Maximum(Date of Vaccination 3 + 28 days at 23:59, scheduled visit 4

			weeks after 3rd vaccination at 23:59)
	29-56 days post dose	One minute after the end of the interval 0-28 days post dose	Min of: 
 • 23:59 at date of last contact (for discontinuations) • 23:59 at date of DB cut-off for interim analyses • Date Vaccination 3 + 56 days at 23:59
	57 days - 6 months post-dose	One minute after the end of the interval 29-56 days post dose	Min of: 
 • 23:59 at date of last contact (for discontinuations) • 23:59 at date of DB cut-off for interim analyses • Maximum(Date of Vaccination 3 + 183 days at 23:59 , day 547 visit at 23:59)
	>6 months post-dose	One minute after the end of the interval 57 days - 6 months post-dose	Min of: 
 • 23:59 at date of last contact (for discontinuations/completions) • 23:59 at date of DB cut-off for interim analyses

Only for participants who did not receive the 2nd dose, but who received the 3rd one.

* only applicable for cohort 1, and for participant of cohort 2 who have received a 3rd dose

SR1004 cohort 3

Dose	Interval	From	to
Post-vaccination 1	0-28 days post dose	Date time of the 1 st vaccination	Min of: 
 • 23:59 at the date of last contact (for discontinuations) • 23:59 at date of DB cut-off for interim analyses • Maximum(Date of Vaccination 1 + 28 days at 23:59 , date of scheduled visit 4 weeks after 1st vaccination at 23:59)
	29-56 days post dose	One minute after the end of the interval 0-28 days post dose	Min of: 
 • 23:59 at date of last contact (for discontinuations) • 23:59 at date of DB cut-off for interim analyses • Date of Vaccination 1 + 56 days at 23:59

	57 days - 6 months post-dose	One minute after the end of the interval 29-56 days post dose	Min of: 
 • 23:59 at date of last contact (for discontinuations) • 23:59 at date of DB cut-off for interim analyses • Maximum of (Date of Vaccination 1 + 183 days at 23:59 , date of scheduled visit 183 days post 1st vaccination at 23:59)
	>6 months post-dose	One minute after the end of the interval 57 days - 6 months post-dose	Min of: 
 • 23:59 at the date of last contact (for discontinuations) • 23:59 at the date of DB cut-off for interim analyses • 1 min prior to date time of vaccination 2
Post-vaccination M12	0-28 days post dose	Date time of the 2nd vaccination	Min of: 
 • 23:59 at the date of last contact (for discontinuations) • 23:59 at date of DB cut-off for interim analyses • Maximum(Date of Vaccination 2 + 28 days at 23:59 , date of scheduled visit 4 weeks after 2nd vaccination at 23:59)
	29-56 days post dose	One minute after the end of the interval 0-28 days post dose	Min of: 
 • 23:59 at date of last contact (for discontinuations) • 23:59 at date of DB cut-off for interim analyses • Date of Vaccination 2 + 56 days at 23:59
	57 days - 6 months post-dose	One minute after the end of the interval 29-56 days post dose	Min of: 
 • 23:59 at date of last contact (for discontinuations) • 23:59 at date of DB cut-off for interim analyses • Maximum (Date of Vaccination 2 + 183 days at 23:59 , day 547 visit at 23:59)
	>6 months post-dose	One minute after the end of the interval 57 days - 6 months post-dose	Min of: 
 • 23:59 at the date of last contact (for discontinuations) • 23:59 at the date of DB cut-off for interim analyses

			
 1 min prior to date time of vaccination 3
Post-vaccination M24	0-28 days post dose	Date time of the 3rd vaccination	Min of: 
 23:59 at the date of last contact (for discontinuations) 23:59 at date of DB cut-off for interim analyses Maximum(Date of Vaccination 3 + 28 days at 23:59 , date of scheduled visit 4 weeks after 3rd vaccination at 23:59)
	29-56 days post dose	One minute after the end of the interval 0-28 days post dose	Min of: 
 23:59 at date of last contact (for discontinuations) 23:59 at date of DB cut-off for interim analyses Date of Vaccination 3 + 56 days at 23:59
	57 days - 6 months post-dose	One minute after the end of the interval 29-56 days post dose	Min of: 
 23:59 at date of last contact (for discontinuations) 23:59 at date of DB cut-off for interim analyses Maximum of (Date of Vaccination 3 + 183 days at 23:59 , day 912 visit at 23:59)
	>6 months post-dose	One minute after the end of the interval 57 days - 6 months post-dose	Min of: 
 23:59 at the date of last contact (for discontinuations) 23:59 at the date of DB cut-off for interim analyses

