2. GENERAL ANALYSIS DEFINITIONS

2.1. Study phases

A baseline (or reference) value will be defined as the value of the last available assessment prior to the first vaccination on Day 1.

The safety analysis will present all results by period, except the serious adverse events (SAE) that will be presented by phase and period (See Section 0). Immunogenicity results will be presented per scheduled time point as appropriate. Listings will be shown per phase and time point.

Study day or relative day is defined as follows:

Study Day = visit date - date of Day 1 + 1; if visit date \geq date of Day 1 (date of first vaccination).

Study Day = visit date - date of Day 1; if visit date $<$ date of Day 1 (date of first vaccination).

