2.1.1. Phase definitions

The phases in the study will be constructed as follows for all groups:

Table 1: Phase Definitions of Cohort 1, 2 and 3

Phase	Phase number	Period	Period number	Interval	
				From	To
Screening	1			00:00 of the date of signing the informed consent form ^a	One minute prior to Dose 1 on Day 1
Regimen	2	Post-Dose 1	1	Date and time of Dose 1 (Day 1)	Minimum of: 
 a) 23:59 at the date of database cut-off b) Maximum (28 days after first vaccination at 23:59, scheduled visit 4 weeks after first vaccination at 23:59) c) 23:59 at the date of last contact (for early discontinuation of the study)
Follow-Up 1	3			1 minute after end of Post-Dose 1 period	Minimum of: 
 a) 23:59 at the date of database cut-off b) One minute prior to date and time of the next vaccination c) 23:59 at the date of last contact (for completed and early discontinuation of the study)

Table 1: Phase Definitions of Cohort 1, 2 and 3

Phase	Phase number	Period	Period number	Interval	
				From	To
Regimen	2	Post-Dose 2	2	Date and time of Dose 2 (Day 57)	Minimum of: a) 23:59 at the date of database cut-off b) Maximum (28 days after second vaccination at 23.59, scheduled visit 4 weeks after second vaccination at 23:59) c) 23:59 at the date of last contact (for early discontinuation of the study)
Follow-Up 2	4			1 minute after end of Post-Dose 2 period	Minimum of: a) 23:59 at the date of database cut-off b) One minute prior to date and time of the next vaccination c) 23:59 at the date of last contact (for completed and early discontinuation of the study)
Regimen	2	Post-Boost (Month 12)	3	Date and time of Month 12 Boost	Minimum of: a) 23:59 at the date of database cut-off b) Maximum (28 days after the Month 12 boost vaccination at 23.59, scheduled visit 4 weeks after the Month 12 boost vaccination at 23:59) c) 23:59 at the date of last contact (for early discontinuation of the study)
Follow-Up Boost (Month 12)	5			1 minute after end of Post-Boost (Month 12) period	Minimum of: a) 23:59 at the date of database cut-off b) One minute prior to date and time of the next vaccination c) 23:59 at the date of last contact (for completed and early discontinuation of the study)

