Regimen	2	Post-Boost (Month 24)	4	Date and time of Month 24 Boost	Minimum of: a) 23:59 at the date of database cut-off b) Maximum (28 days after the Month 24 boost vaccination at 23.59, scheduled visit 4 weeks after the Month 24 boost vaccination at 23:59) c) 23:59 at the date of last contact (for completed and early discontinuation of the study)

Table 1: Phase Definitions of Cohort 1, 2 and 3

Phase	Phase number	Period	Period number	Interval	
				From	To
Follow-Up Boost (Month 24)	6			1 minute after end of Post-Boost (Month 24) period	Minimum of: a) 23:59 at the date of database cut-off b) 23:59 at the date of last contact (for completed and early discontinuation of the study)

^a in case an earlier date is available (eg. for lab or vital signs), then use the very first date to include all data

In case the one-dose regimen is selected (Groups 11 through 16 from Cohort 2) after the evaluation of Cohort 2, then the post dose 2 and follow up 2 will not be applicable.

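### An unsolicited AE with no start date at all defaults to the post-dose 1 period, even when it is first recorded after a later dose

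*SAP*

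**What the plan says.** SAP 5.1.3, Step 1 places unsolicited AEs in periods by start date and has two separate rules for incomplete start dates.

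- **Partly missing:** "the events are allocated to the periods using the available partial information on start and end date; no imputation will be done". The SAP accepts the consequence: "This rule may lead to multiplication of the event as a consequence of its assignment to multiple periods".
- **Completely missing:** "In case of a completely missing start date, the event is allocated to the first active phase (post dose 1 period"), with one exception: "except if the end date of the AE falls before the start of the first active phase (post dose 1 period").

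The second rule does not use the visit of recording, the most recent vaccination, or an end date after dose 1.

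SAP Table 1 (2.1.1) ends post-dose 1, before capping at database cut-off or last contact, at "Maximum (28 days after first vaccination at 23:59, scheduled visit 4 weeks after first vaccination at 23:59"). It then defines separate active periods after dose 2, the Month 12 boost and the Month 24 boost. The last of these begins at "Date and time of Month 24 Boost".

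SAP 2.1 presents safety by period, "except the serious adverse events (SAE) that will be presented by phase and period". For potential AESIs, "attribution to the intervals will be done similarly to the unsolicited AEs as described in Section 5.1.3 above".

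**The concern.** The default suits a single-dose study, where it makes sure that an undated event counts as treatment-emergent. Here most participants are dosed two or three times, and non-serious AEs are collected in a separate 28-day window after each dose (protocol 12.3.1). If an event first appears in a later window, its place in the sequence of doses is informative, and the rule discards it. For the booster the default is then not cautious, because the event leaves the booster's numerator.

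Booster safety and reactogenicity is part of the primary objective in Cohorts 1 and 3 (protocol 2.1). Three consequences follow from the design:

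- In Cohort 3 Group 20 (one-dose schedule), an undated event first recorded after the Month 12 placebo would be counted after the active first dose.
- The Cohort 3 primary analysis for a one-dose regimen covers data to Day 29 (protocol 11.6.3). An undated event recorded after a booster would later be added to a period already reported.
- For the AESI tables (embolic and thrombotic events, thrombocytopenia), time since dose is the purpose of the display. An undated event recorded late would appear in the 0-28 day row after dose 1.

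**Working it through.** The plan states no figure on this point, so there is none to reproduce. The check is a reading of the rule against the dosing schedule, followed by the size of one misplaced event.

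**1. The rule applied to possible cases**

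| Event | Result under SAP 5.1.3 |
|---|---|
| Cohort 1, Group 9: no start date, first recorded at the visit 28 days after dose 2 | Post-dose 1 |
| Cohort 3, Group 20: no start date, first recorded 28 days after the Month 12 placebo | Post-dose 1 (active dose) |
| Cohort 3, Group 19: no start date, first recorded 28 days after the Month 24 dose | Post-dose 1, although that dose is planned 730 − 1 = 729 days after dose 1 |
| Any group: only month and year of start known | Every period that matches; not defaulted |
| Any group: no start date, end date before dose 1 | Not post-dose 1 |

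The first three rows are the problem. The exception in the last row does not reach them.

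**2. Link to SAP 5.1.1.** That section limits the unsolicited AE tables, SAEs apart, to events whose start date lies within 28 days after vaccination. It does not say how an undated event meets this condition. If it is admitted through 5.1.3, it adds to post-dose 1. If it is not, it is left out of the tables. Under both readings the later period loses it; only the gain in post-dose 1 depends on the reading.

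**3. Size of one participant.** Inputs: group sizes 8 (protocol Table 8), 135 and 45 (protocol Table 10).

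- 1/8 = 12.5 percentage points
- 1/135 = 0.74 points
- 1/45 = 2.2 points

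SAP 5 uses the number with data in the period as denominator. With dropout the later-period shift is slightly larger.

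**4. Illustration for Group 19 (n = 135).** The documents give neither the AE risk per period, r, nor the share of AEs with no start date at all, m. I assume r = 10% to 30% and m = 0.5% to 5%, and count one event per affected participant.

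- Participants leaving each booster period: n × r × m
- Observed booster-period risk: r × (1 − m)
- Upper bound for post-dose 1 if both boosters lose events to it: r + 2 × r × m

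| r | m | Leaving each booster period | Month 24 period shows | Post-dose 1 shows at most |
|---|---|---|---|---|
| 10% | 0.5% | 135 × 0.10 × 0.005 = 0.07 | 9.95% | 10.1% |
| 20% | 1% | 135 × 0.20 × 0.01 = 0.27 | 19.8% | 20.4% |
| 30% | 5% | 135 × 0.30 × 0.05 = 2.0 | 28.5% | 33.0% |

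For common events the shift is small over the whole assumed range.

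**The case against.** The case for leaving the rule alone is considerable.

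- **Narrow scope.** Only a completely missing start date triggers the default. A reader might infer that every incomplete date goes to dose 1. The documents do not support that: partial dates are matched on what is known, and can add to a booster count. This stands.
- **Possibly an empty category.** The eCRF is reviewed for completeness and queries can be raised (protocol 17.5, 17.6). SAEs are reported within 24 hours (protocol 12.3.2). This stands, so nothing shows that any count will actually be wrong.
- **Other displays.** Severe and serious AEs get listings or narratives as appropriate (SAP 5.1.2), and SAEs are tabulated over the whole study (SAP 5.1.1). Whole-study SAE counts are unchanged and no formal group comparison is made. This limits the harm but does not correct the by-period or AESI-interval tables.
- **Recording is not onset.** An SAE first recorded in long follow-up, or an event noted pre-dose on a vaccination day, need not belong to the 28 days after the latest dose. This stands, and any replacement rule must deal with it.
- **Data availability.** The documents do not state that AE records carry the visit or date of first recording. This stands as a condition on the fix.
- **Group 20.** Moving an event from placebo to active counts against the vaccine, which is the cautious direction. That is true for dose 1, but the Month 12 placebo period is still under-stated as a reference.

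**Conclusion.** The rule as written gives the wrong period in an identifiable case: no start date at all, and first recorded after a later dose. The direction is fixed: the later period loses the event and post-dose 1 gains it. SAEs by period and AESI intervals are affected in the same way.

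The effect is conditional and probably small. The number of such events is not given and may be zero. One event is worth 12.5 points in a group of 8 and 0.7 points in a group of 135. Under the assumed ranges, between 0.07 and 2.0 of 135 participants would leave each booster period. It matters mainly for rare SAEs and AESIs, where one event can be the entire content of a row.

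A reader might go further and infer that booster AE rates are under-counted in this trial, or that a serious signal would be lost. Neither follows, because no undated events are documented and serious events also appear in other displays. Nor is the displacement always a matter of years: that describes only the Month 24 dose in Cohort 3. Cohort 1 has its booster at Month 12, and the current Cohort 2 schedule has no dose after Day 57. SAP Table 1 has four active periods, but no planned group receives four doses.

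**What to change.** Replace the completely-missing-start-date rule in SAP 5.1.3, Step 1 as follows:

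- Where the visit or date of first recording is available, allocate the event to the post-dose period of the most recent vaccination before that recording.
- Treat an event recorded pre-dose on a vaccination day as belonging to the preceding cycle.
- Never allocate an event to a period that starts after its end date, and keep the exception for an end date before dose 1.
- Use post-dose 1 only if the time of recording is unknown.

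Apply the same rule to the AESI intervals. Flag and list every AE with a completely missing start date. The list should include SAEs first recorded in follow-up, with a note that their 28-day allocation is a conservative convention. State in SAP 5.1.1 that these events enter the tables under this rule.

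The cost is a few lines of SAP text and a short derivation, which depends on the recording visit or date being held in the database. The downside is that some follow-up SAEs may be counted in a 28-day period; the flag and the list make these visible.

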- Solicited local AEs: erythema (measured using the ruler supplied), swelling/induration (measured using the ruler supplied and graded using the functional scale), and pain/tenderness.
- Solicited systemic AEs: fatigue, headache, myalgia, arthralgia, chills, nausea, and fever (ie, body temperature ≥ 38.0 °C).

Body temperature (oral route preferred) should be measured at approximately the same time each day, preferably in the evening, using the thermometer supplied. All diary assessments, including body temperature, 7 days after each vaccination may be collected earlier in the day to coincide with the clinic visit.

Unsolicited AEs will be collected for 28 days after each vaccination (ie, from the time of each vaccination through the following 28 days).^a SAEs will be collected from first dose administration to the end of the double-blind phase of the study. During the long-term follow-up phase (Groups 14 and 15 from Cohort 2), only SAEs related to study vaccine, study procedures, or non-investigational (concomitant) Janssen products, and all AEs leading to discontinuation will be collected. All AEs, including any that are ongoing at 28 days after each dose, will be followed until clinical resolution or stabilization. Concomitant medications will be collected from the time of each vaccination, through 28 days after each vaccination, and additionally outside these periods when associated with any SAE. During the long-term follow-up phase (Groups 14 and 15 from Cohort 2), only medications in conjunction with SAEs related to study vaccine, study procedures, or non-investigational (concomitant) Janssen products, or in conjunction with AEs leading to discontinuation should be recorded.

All SAEs and AEs leading to discontinuation from the study/vaccination (regardless of the causal relationship) are to be reported from the moment of first vaccination until completion of the participant's last study-related procedure, which may include contact for safety follow-up.

^a AEs that start more than 28 days after a vaccination, but that are still present at the time of the next vaccination will also be recorded.

STATISTICAL METHODS

Sample Size Determination

For Cohort 1, no formal sample size calculations are done.

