5.1. Adverse Events (AE)

5.1.1. Definitions

Solicited AEs shown in the tables and listings will be extracted from the SDTM CE domain which will be based on the diary pages and onsite assessment pages of the CRF ([ATTACHMENT 2](#)). When participants are given two injections in opposite arms at a given visit, then local solicited AEs will be collected and reported for both arms separately. For unsolicited AEs, only AEs with start date (grade and/or relation) within the 28-day period following vaccination will be presented in the safety tables except for SAEs, which will be captured and tabulated in the outputs covering the whole study period. All other unsolicited adverse events collected outside this 28-day period will be presented through listings. Any RTI recorded as an AE in the eCRF will be excluded from any AE analysis if the central laboratory RT-PCR is subsequently found to be positive for RSV.

Solicited local AEs will be by definition considered as related to the study vaccine.

The severity of the AEs will be classified as grade 1 to 4. Solicited events that are graded less than grade 1, are not considered as AE.

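### SAP 5.1.3: an adverse event with no end date can pull a same-term SAE from the next follow-up phase back into the post-dose period, with the earlier onset

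*SAP*

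**What the plan says.** SAP 5.1.3 works in two steps. Step 1 allocates each unsolicited AE to a period by its start date and time. Where no end date is given at all, Step 1 fills in the analysis cut-off if the participant has not yet left or finished; otherwise the gap is filled "by the end date of the last period for subjects who discontinued or completed the trial". Partial dates are not imputed.

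Step 2 combines overlapping or consecutive events, defined as "events of the same subject with the same preferred term which have at least 1 day overlap", or where the second starts the day after the first ends. Rule 3 covers a post-dose period followed by a follow-up phase: "In case overlapping/consecutive events start in both an active period followed by a non active period, they are allocated to the active period only". The records count as one AE. Each stays in ADaM, but with a common onset, period and duration. Rule 1 keeps a non-active event followed by an active one separate. Rule 4 does the same for events in two active periods or in non-consecutive periods.

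Remark 1 allows combining only when start and stop dates are known. Remark 2 then adds: "In case the completely missing end date is imputed (for period allocation), this date is also considered as a complete date".

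SAP 2.1 presents SAEs by phase and period. The AESI part of 5.1.3 applies the same Step 2 rules to time intervals, treating 0-28 days as active and all later intervals as non-active.

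**The concern.** A missing end date says little about whether an AE was still present months later. The protocol (synopsis, Safety Evaluations; also 3.1.2) states that "All AEs, including any that are ongoing at 28 days after each dose, will be followed until clinical resolution or stabilization", so a stabilized AE can be left with no end date. Remark 2 turns that gap into an overlap with whatever same-term event follows in the next phase, and rule 3 then overrides the reported start date that Step 1 would have used.

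The shift goes one way. Rule 3 moves follow-up events into the vaccine window, while rule 1 prevents the reverse. Outside the 28-day windows the study collects mainly SAEs, so they are the records most exposed. The treatment of incomplete dates is also uneven: a partly known end date cannot support a merge (Remark 1), but a wholly unknown one can.

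At stake is the apparent timing of SAEs after vaccination, in outputs laid out to show it. The AESI intervals for embolic, thrombotic and thrombocytopenic events have the same purpose.

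**Working it through.** The plan gives no figure to reproduce, so the rules were applied to the periods of SAP Table 1. Assumptions: visits on scheduled days (protocol Schedules of Activities), and each post-dose period ending 28 days after the dose. Table 1 extends it to the 4-week visit if that is later.

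**One case, Cohort 3 one-dose schedule.** Post-Dose 1 is Days 1-29 and Follow-Up 1 is Days 30-364. A non-serious Grade 1 AE starts on Day 20 with no end date. A Grade 3 SAE with the same term starts on Day 250.

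- Step 1: the first AE's end becomes the cut-off, which cannot precede Day 250 if the SAE is in the data, or the end of the last period. For a completer with all three doses that is Day 758 or Day 1095, depending on the reading below. Both are after Day 250.
- Remark 2: the imputed date counts as complete, so the events overlap.
- Rule 3: both records go to Post-Dose 1 with onset Day 20. Error: 250 − 20 = 230 days.
- With a reported end date of Day 24, the events neither overlap nor follow on (24 + 1 = 25, not 250). The SAE stays in Follow-Up 1 with onset Day 250.

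**Which sequences merge.** The first event has no end date and starts in a post-dose period; the second starts in a later follow-up phase. Largest back-dating = last day of follow-up − first day of post-dose period.

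| Cohort | Sequence | Largest back-dating |
|---|---|---|
| 1 | Post-Dose 1, Follow-Up 1 | 56 − 1 = 55 days |
| 1 | Post-Dose 2, Follow-Up 2 | 364 − 57 = 307 days |
| 1 | Month 12 boost, its follow-up | 730 − 365 = 365 days |
| 2 | Post-Dose 1, Follow-Up 1 | 56 − 1 = 55 days |
| 2 | Post-Dose 2, Follow-Up 2 | 730 − 57 = 673 days (Groups 14-15: 1095 − 57 = 1038 days) |
| 3 | Post-Dose 1, Follow-Up 1 | 364 − 1 = 363 days |
| 3 | Month 12 boost, its follow-up | 729 − 365 = 364 days |
| 3 | Month 24 boost, its follow-up | 1095 − 730 = 365 days |

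That is 3 of 6 possible pairs in Cohort 1, 2 of 3 in Cohort 2 and 3 of 6 in Cohort 3. The other pairs, such as Post-Dose 1 with the Month 12 follow-up, stay separate under rule 4.

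**Meaning of the last period.** Table 1 numbers only the post-dose intervals as periods, yet Step 2 rule 1 calls follow-up a non-active period. If Step 1 means the last numbered period, a completer's imputed date is Day 85 in Cohort 2 and Day 758 in Cohort 3. The merge into the final follow-up then catches only an event starting the next day: 86 − 57 = 29 and 759 − 730 = 29 days. Merges in earlier follow-ups are unchanged.

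**AESI intervals, Cohort 3.** The 0-28 day interval merges only with 29-56 days. Largest back-dating: 57 − 1 = 56 days after dose 1 and 421 − 365 = 56 days after the Month 12 boost. Later intervals are non-consecutive and stay separate.

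**Size.** The documents give no rate of missing end dates or of repeat same-term SAEs. As illustration only, assume that 20-40% of participants have an unsolicited AE per dose, 5-25% of those have no end date, and 1-5% of those have a later same-term SAE. Per 135 participants per dose this gives 135 × 0.20 × 0.05 × 0.01 = 0.01 to 135 × 0.40 × 0.25 × 0.05 = 0.7 misplaced SAEs. One such SAE turns 0/135 into 1/135 (0.7%) in the post-dose column.

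**The case against.** An AE with no end date is often truly ongoing. Treating a later same-term record as its worsening is a defensible convention and errs towards attributing events to the vaccine window. Remark 2 is also a deliberate statement of when an imputed date counts as known, so it does not contradict Remark 1. Both points stand, and they argue against deleting Remark 2. They do not justify replacing an SAE's reported start date when the only evidence of continuity is a blank field.

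A reader might infer that the rule contradicts SAP 5.1.1: "For unsolicited AEs, only AEs with start date (grade and/or relation) within the 28-day period following vaccination will be presented in the safety tables". That sentence goes on to exempt SAEs, which are tabulated over the whole study. There is no direct conflict for SAEs; it arises only for non-serious events starting after the window, which 5.1.1 sends to listings.

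A reader might also infer that any later same-term event is absorbed up to study end. Rules 1 and 4 rule that out. Nor do the documents firmly support the 1038-day extreme. For completers it depends on how the last period is read. It also follows a placebo dose on Day 57 in Groups 14-15, whose long-term follow-up collects only SAEs related to study vaccine, study procedures or concomitant sponsor products, and AEs leading to discontinuation.

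Finally, safety is descriptive, the pausing rules (protocol 11.9) do not use these derived periods, and listings or narratives are provided for serious AEs as appropriate. All true. But SAP 2.1 shows listings per phase, and the SAP does not say whether they display reported or derived onset.

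**Conclusion.** The concern holds in a limited form. A post-dose AE with a completely missing end date absorbs a same-term event from the directly following follow-up phase, and a follow-up SAE can then be shown in the post-dose period with the earlier onset. In Cohort 3 the onset can be wrong by up to about a year (363 to 365 days; 29 days instead of 365 in the final follow-up for completers on the narrower reading). The AESI intervals carry the same fault, up to 56 days.

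It would be wrong to conclude that the primary SAE endpoint is miscounted. That endpoint covers SAEs from first dose to study end, and the total does not change; what changes is the phase and the onset. Misplacements are probably few, but this rests on assumed rates. The day figures assume scheduled visit days.

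**What to change.** Add one sentence to SAP 5.1.3, Step 2: when a merge relies on an imputed end date, a contributing record that is serious, or of higher grade than the first, keeps its own reported start date and its own phase or interval in the SAE, Grade 3 and AESI tables and listings. Add a second to Step 1 stating whether the last period means the last post-dose period or includes the follow-up phase after it.

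Remark 2 can stay for other purposes. Merges based on reported end dates are untouched, so a documented worsening of an AE that began in the window is still shown there.

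The cost is two sentences and a small ADaM change. The downside is that one long-running condition may appear once in the post-dose period and once in follow-up.
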